Cognitive Behavioral Therapy for Insomnia (CBT-I). Participants assigned to the CBT-I condition will attend 1-hour individual sessions of CBT-I once a week for five weeks. A sixth week of treatment will be included – and scheduled for the same date as the post-treatment assessment – if the participant and research team agree that it would be beneficial (e.g., if a participant has difficulty grasping cognitive therapy concepts). Zoom video service will be utilized for remote appointments when necessary. Consistent with clinical guidelines (Schutte-Rodin, Broch, Buysse, Dorsey, & Sateia, 2008), treatment will include stimulus control (e.g., limit use of bed to sleep or sexual activity, get out of bed if lying awake for more than 20 minutes), sleep restriction (limit time in bed to amount of time spent sleeping on a typical night), sleep hygiene (e.g., avoid exercise within 2 hours of bedtime, create cool and dark sleep environment), relaxation training, and cognitive restructuring. All patient interactions will be conducted under the weekly supervision of [name], a licensed clinical psychologist who specializes in addiction treatment. In turn, [name] will be supervised by [name], a licensed clinical psychologist who is board certified in behavioral sleep medicine.

Sleep hygiene. All participants will receive a one-page handout on sleep hygiene that includes personalized normative feedback on their alcohol use. This is the only intervention that participants assigned to the Sleep Hygiene condition will receive and is consistent with what may be expected as standard care in a doctor's visit with a primary care physician. A sleep coach will then call to check in on sleep hygiene participants' progress each week for five weeks. We did not include a control condition that was matched with CBT-I for time and content, given our focus on preliminary outcomes.

Personalized normative feedback on alcohol use. As part of the sleep hygiene recommendations, participants will receive personalized normative feedback on their alcohol use. Normative feedback will be modeled after previously utilized, efficacious interventions (Pedersen, Parast, Marshall, Schell, & Neighbors, 2017). Feedback will portray a bar graph and explanatory text comparing personal drinking quantity to that of same-sex peers.

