Follow-up assessments. To enhance follow-up rates, participants will receive up to \$300 for completion of all phases of this study. The proposed payment schedule is as follows:

Baseline		Up to \$70
Clinical interview (Zoom)	60-90min	\$0
Online survey	30-45min	\$30
14 days of actiwatch	---	\$20
14 consecutive diaries	2-3min/day	
-7 in a row to be eligible		needed for eligibility, \$0 bonus
-10 in a row		\$10 bonus
-14 in a row		\$20 bonus
Mid-Treatment		Up to \$20
Online survey	10-15min	\$20
Post-Treatment		Up to \$80
Online survey	30-45min	\$20
-phone only	5min	\$10
14 days of actiwatch	---	\$30
14 consecutive diaries	2-3min/day	

-7 in a row		\$10
-10 in a row		\$20
-14 in a row		\$30
3-Month Follow-Up		Up to \$130
Online survey	30-45min	\$50
-phone only	5min	\$20
14 days of actiwatch	---	\$40
14 consecutive diaries	2-3min/day	
-7 in a row		\$10
-10 in a row		\$20
-14 in a row		\$40

Participant retention. To enhance follow-up rates, participants will receive up to \$70 for completion of the baseline, \$20 for the mid-treatment assessment, up to \$80 for the post-treatment assessment, and up to \$130 for the 3-month follow-up; for a total of up to \$300. They will also receive reminder texts/calls, have access to free parking outside the research lab, receive immediate payment, and have access to after-hours ‘on-call’ support. We will also send all participants a personalized “thank you” note following study completion.

Blinding. [name] will not be blinded to block size or participant assignment because she will inform study therapists of participant assignment to conditions. However, [name] and study therapists will be blinded to assessment outcomes, and the assessment RA will be blinded to participant condition. All participants will be told that they are receiving treatment for insomnia in order to blind them to condition assignment (sleep hygiene will be described as “brief” insomnia treatment, and CBT-I will be described as the “most intense” treatment).

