Early stopping rules. [name] will monitor adherence to the study protocol and adverse events on an ongoing basis and discuss these issues with the research team during weekly meetings. All serious and unexpected adverse events will be reported to the IRB within 24 hours of receipt of information. Other adverse or potentially adverse events will be monitored and reported at annual continuing reviews. After discussion with the IRB, we will discontinue the trial if there is (a) compelling evidence from this or another study of a serious adverse effect of CBT-I that has potential to override potential benefit, (b) compelling evidence from this or another study of a significant beneficial effect of CBT-I, such that continued denial to other groups would be unethical, or (c) low probability of addressing study aims within a feasible time frame.

8. Risks

We believe the risks associated with completing assessments and participating in the intervention are minimal. Potential risks include: temporary daytime fatigue (due to restriction of time in bed), subjective discomfort from answering questionnaires, coercion, and the possibility of a breach of confidentiality. Participants will not incur financial risk. There are no other known iatrogenic effects of CBT-I or completion of sleep diaries. However, if any emerge, they will be addressed immediately by research and/or clinical staff.

The following safeguards will be implemented to protect participants from risks related to study participation:

Temporary fatigue. Participants will be informed as part of the consent process that restricting their time in bed may increase daytime fatigue for the first few weeks of treatment (although this will be temporary, as time in bed will be expanded as sleep efficiency improves). Consistent with standard insomnia treatment procedures, time in bed will never be restricted to less than 5 hours in order to avoid impaired vigilance and significant daytime sleepiness. Participants will also be provided with recommendations on ways to increase alertness and counter daytime fatigue (e.g., staying active, engaging in social activities, strategic use of caffeine and water).

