there may be a change to the benefit-to-risk ratio of research participation; and (c) procedures to protect participant privacy and confidentiality. She will monitor all serious, unexpected, and other adverse or potentially adverse events. Serious adverse events include those resulting in death, inpatient hospitalization, a threat to life, persistent or significant disability or incapacity, congenital anomalies/birth defects, or serious health risk. Unexpected adverse events are those that were unforeseen based on the anticipated potential risks outlined in the study protocol and informed consent. Other adverse or potentially adverse events include those that may be causally related to study participation and lead to participant distress or drop-out.

[name] will monitor data quality and adverse events on an ongoing basis and discuss these issues with the research team during weekly meetings. All serious and unexpected adverse events will be reported to the IRB within 24 hours of receipt of information. Other adverse or potentially adverse events will be monitored and reported at annual continuing reviews.

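### Daytime fatigue, the only physical harm on the protocol's risk list, has no clear adverse-event category and no common method of collection in the two arms

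*Combined protocol and SAP*

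**What the plan says.** The data safety and monitoring plan in section 8 (Risks) sets up three groups of events.

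- Serious: "Serious adverse events include those resulting in death, inpatient hospitalization, a threat to life, persistent or significant disability or incapacity", with two further outcomes added after these.
- Unexpected: "Unexpected adverse events are those that were unforeseen based on the anticipated potential risks outlined in the study protocol and informed consent".
- Other: "Other adverse or potentially adverse events include those that may be causally related to study participation and lead to participant distress or drop-out".

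The monitor's remit covers all three: "She will monitor all serious, unexpected, and other adverse or potentially adverse events". Serious and unexpected events go to the IRB within 24 hours. Other events are reported at annual continuing review. The DSMB meets every 6 months and reviews adverse events.

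The opening of section 8 (Risks) states: "Potential risks include: temporary daytime fatigue (due to restriction of time in bed". The remaining listed risks are discomfort from questionnaires, coercion and breach of confidentiality. Under Temporary fatigue, participants are to be told at consent that "restricting their time in bed may increase daytime fatigue for the first few weeks of treatment". The cause lies in one arm: section 4 gives "sleep restriction (limit time in bed to amount of time spent sleeping on a typical night" as a component of CBT-I, while the control arm receives a one-page handout and weekly check-in calls.

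**The concern.** The protocol treats fatigue as a safety matter. It discloses it at consent, sets a floor on time in bed because of it, and offers advice on staying alert. Yet the only event group that could hold ordinary fatigue is described by two joint conditions: a possible link to taking part, and distress or drop-out as a result. Taken as written, that description leaves out a tired participant who carries on.

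The first objective of this pilot is feasibility and acceptability, so how well heavy-drinking Veterans tolerate sleep restriction is part of what it should report. A low fatigue count might reflect the definition and the way events were gathered, not good tolerability. A larger trial planned from this one would inherit that number.

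**Working it through.** No figure in the plan can be reproduced here, so the check is a reading of the text. Take a CBT-I participant with marked daytime fatigue in the first weeks of treatment who keeps attending and reports no distress.

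| Group | Condition in the plan | Does this case fit? |
|---|---|---|
| Serious | Defined by outcome (death, hospital admission, threat to life, disability and similar) | Ordinarily no |
| Unexpected | Not foreseen among the risks in the protocol and consent | No: fatigue is on the list and disclosed |
| Other | Possibly caused by participation, and leading to distress or drop-out | First condition met, second not |

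The case matches no description. The first two groups carry no causal, distress or drop-out condition, so the gap is confined to foreseen, non-serious events.

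**Could another measure supply the information?** None of the outcomes in sections 7a and 7b is described as measuring fatigue or sleepiness. The nearest is the Insomnia Severity Index, which asks how far sleep problems interfere with the day. It enters a total efficacy score and does not isolate fatigue brought on by treatment.

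**Is there a common method of collection?** The available text names no adverse-event form, checklist, severity grade or reporting window. The data analysis part of section 8 (Study Statistics) has no analysis of harms by arm. Contact also differs: five weekly one-hour sessions for CBT-I, and five weekly calls of unstated content for control.

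**What this does to a comparison.** Let p be the true proportion with fatigue in an arm and r the share of those cases that gets recorded. Then

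- recorded cases = n × p × r
- recorded ratio, CBT-I to control = (p1 / p2) × (r1 / r2)

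The ratio is undistorted only if r1 = r2. Nothing in the plan secures that, and the direction of any distortion is unknown: longer contact could raise r in the CBT-I arm, while treating fatigue as an expected part of therapy could lower it. The documents give neither p nor r.

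**Illustration only.** Assume true fatigue of 50% and 20%, with 22 per arm (the abstract's group size) and the same r in both arms. Power is for a two-sided 5% comparison of two proportions by normal approximation.

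| Assumed r | Recorded, CBT-I | Recorded, control | Power |
|---|---|---|---|
| 1 | 22 × 0.50 = 11.0 | 22 × 0.20 = 4.4 | 0.55 |
| 0.5 | 5.5 | 2.2 | 0.25 |
| 0.25 | 2.8 | 1.1 | 0.14 |
| 0.1 | 1.1 | 0.4 | 0.08 |

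Even complete recording would not give a well-powered test. What is at stake is an honest description by arm.

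**The case against.** The strongest reply is that the description of other events opens with the word include, which need not be exhaustive, and that the causal threshold is low, asking only for a possible link. The monitor's remit and the DSMB's review are not limited to a narrow group, both arms have weekly staff contact, and the expected fatigue is temporary, disclosed and mitigated. All of this stands. It makes the text ambiguous and not a strict filter. But if the list is open, the plan then has no rule for foreseen, non-serious events, and staff may differ in what they log. Clarification is needed on either reading.

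The consent form is not in the available text, and a question asked elsewhere cannot be ruled out. Absence here means absence from what can be read.

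A reader might also infer several stronger things that the documents do not support.

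- *Falls, accidents and heavier drinking are lost too.* Falls and accidents are not listed risks, so they would plausibly count as unexpected and be reported within 24 hours. Drinking is measured by the Timeline Followback, the alcohol consequences questionnaire and the diary.
- *Unblinded staff judge causality when they record an event.* Section 4 (Blinding) says one person "will not be blinded to block size or participant assignment because she will inform study therapists of participant assignment to conditions", and that the assessment research assistant is blinded. Nowhere does it say who judges causality, or when.
- *No harms can be compared between arms.* Serious and unexpected events can be tabulated by arm.
- *The DSMB cannot apply its harm criterion.* That criterion concerns a serious adverse effect, and serious events are defined by outcome alone.
- *The undercount is some stated multiple.* Any multiple would simply be the reciprocal of an assumed r.

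**Conclusion.** The point holds in a limited form. Foreseen, non-serious harms have one possible home, and its description requires possible causality together with distress or drop-out. The available text specifies no common collection method and no harms table by arm. Daytime fatigue from time-in-bed restriction may therefore be under-recorded, and a fair comparison between arms is not supported. The size cannot be derived from the documents.

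The conclusion rests on two things: that staff follow the description as written, or differ in how they read it; and that no standard fatigue question exists in material outside the available text. It does not affect the efficacy analyses. It is a change worth making because it is cheap and because tolerability matters to the aims of this pilot.

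**What to change.** 1. Redefine other adverse events as any new or worsened problem, whatever its cause or consequence. Record relatedness in a separate field, judged afterwards.
2. Put the same few items to both arms in the existing mid-treatment, post-treatment and 3-month surveys: daytime sleepiness or fatigue, accidents or near-misses, and an open-text item. Accidents are included so that both arms are asked alike, not because the present categories exclude them. The mid-treatment survey (week 4 in Table 1) falls in the period when fatigue is expected.
3. Consider adding the fatigue item to the baseline survey. Eligibility already requires daytime impairment, so worsening is hard to judge without a starting value.
4. Tabulate events by arm, with numbers of participants and of events, in the 6-monthly DSMB reports and the final report. State that the comparison is descriptive.

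The cost is a short amendment and a few survey items at assessments already planned. The downside is more minor events to log and a less favourable-looking harms table, which the report should explain as the result of asking directly.
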